Part 2. One drop 3 times a day on a randomized eye for 10 (\pm 1) days at home

Part 3. One drop of the randomized product 3 times a day on both eyes for 30 (\pm 2) days at home

Assessments:Safety and ocular tolerability:

Physical examination of the eyes will be performed by the Investigator at screening, in Part 1 at baseline and after the 4th dose, in Parts 2 and 3 at baseline and after the last dose. The Investigator will also evaluate possible local eye reactions visually at visits in all Parts.

Ocular comfort rating using the OSDI questionnaire will be performed at screening, before the 1st treatment in all Parts, and at end-of-study visit in Parts 2 and 3.

AEs will be collected throughout the study.

Efficacy:

OSDI, tear osmolarity, TBUT, blink rate, and corneal and conjunctival staining will be measured at screening, before the 1st treatment in all Parts, and at end-of-study visit in Parts 2 and 3.

Statistical methods:

Descriptive statistics by treatment group and visit day will be provided to summarize the results. Also changes from baseline will be summarized with descriptive statistics. No imputations will be done for missing observations. If not stated otherwise, a two-sided p-value less than 0.05 will be considered statistically significant. Changes in OSDI scores in Part 3 will be compared by treatment groups using analysis of variance model. No interim analyses are planned.

ABBREVIATIONS AND DEFINITION OF TERMS

ADE	adverse device effect
AE	adverse event
CRF	case report form
D	day
EC	ethics committee
FDA	Food and Drug Administration
GCP	good clinical practice
ETDRS	early treatment diabetic retinopathy study
IB	investigator's brochure
IBI	interblink interval
IER	Institute of Eye Research
IOP	intraocular pressure
ITF	investigator's trial file
OPI	ocular protection index
OSDI	ocular surface disease index
ITT	intent-to-treat
PP	per-protocol
SADE	serious adverse device effect
SAE	serious adverse event
SAP	statistical analysis plan
SD	standard deviation
TBUT	tear film break-up time
TFOS DEWS II	Tear Film and Ocular Surface Society's Dry Eye Workshop II
USADE	unanticipated serious adverse device effect

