7.2.3. Statistical hypotheses

The main objective of the study is to evaluate ocular safety and tolerability in 3 different study Parts conducted sequentially. For the study part 3 a sample size calculation was conducted with OSDI as the parameter of interest. The evaluation of the study will be based on the total evidence collected, not only this single parameter in one Part which was used for sample size calculation.

However, for OSDI in Part 3, the following statistical hypothesis will be tested:

H₀: There is no difference between study products in OSDI scores.

H₁: There is a significant difference in OSDI scores in favour of the investigational product.

Statistical analyses will be performed primarily on the ITT population. The PP population will be used as a secondary dataset.

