7.2.5. Analysis of study variables

Demographic and baseline characteristics of the subjects will be tabulated with descriptive statistics. The disposition of the subjects (and eyes) will be summarized.

The safety population having received the study treatment and with any follow-up data will be considered evaluable for safety and tolerability for the corresponding Part of the study. AEs will be summarized for each treatment group and study Part by severity, causality, and duration. Ocular AEs will be reported separately. All SAEs will be listed with all relevant information.

In Part 1, the ocular safety and tolerability of trehalose emulsion eye drops will be evaluated as a within-subject comparison to the untreated eye and to baseline. In Part 2, the evaluation will be performed as a within-subject comparison to the control eye and to baseline. In Part 3, the evaluation will be performed between subjects receiving trehalose emulsion eye drops in comparison with subjects receiving control eye drops and to baseline.

Physical examination of the eye parameters will be summarized descriptively by eye in all Parts of the study. The ocular safety and tolerability of the treatments evaluated at the end-of-study visit will be summarized by study day, treatment and eye. In addition, ocular comfort ratings (OSDI) by the subjects will be summarized by study day and treatment (Parts 2 and 3).

The comparisons between treatments in Part 2 will be conducted using standard statistical methodology for paired data (e.g. paired t-test for continuous variables and Wilcoxon signed rank test for variables in ordinal scale). The comparisons between treatments in all ocular measurements (including biomarkers and physical examination of eye parameters) in Part 3, which are the primary basis of evaluation of study objectives, are done with statistical methods appropriate for parallel group design. Analysis of variance technique will be used to evaluate the difference in the change in OSDI between treatment groups. Wilcoxon rank sum test will be used for ordinal scale variables (e.g. staining and redness). Details of all methods and the testing strategy will be provided in the SAP finalized before the database lock and randomization code opening.

Concomitant medications will be listed.

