## 2 Study objective(s)

The study is comprised of three parts. Part 1 of the study aims to investigate safety and ocular tolerability of trehalose emulsion eye drops. Primary objective of Part 1 of the study is:

*to evaluate the safety and ocular tolerability of trehalose emulsion eye drops administered on one eye four times a day for one day.*

Part 2 of the study aims to investigate the safety, ocular tolerability and efficacy of trehalose emulsion eye drops administered for 10 days compared to control eye drops. Primary objective of Part 2 of the study is:

*to evaluate the safety, ocular tolerability and efficacy (OSDI, tear osmolarity, tear film break-up time) of trehalose emulsion eye drops administered on both eyes three times a day for 10 days as a change from baseline and compared to control eye drops.*

The secondary objective of Part 2 of the study is:

*to evaluate the efficacy (blink rate, corneal and conjunctival staining) of trehalose emulsion eye drops administered on both eyes three times a day for 10 days as a change from baseline and compared to control eye drops.*

Part 3 of the study aims to investigate the safety, ocular tolerability and efficacy of trehalose emulsion eye drops administered for 30 days compared to control eye drops. Primary objective of Part 3 of the study is:

*to evaluate the safety, ocular tolerability and efficacy (OSDI, tear osmolarity, tear film break-up time) of trehalose emulsion eye drops administered on both eyes three times a day for 30 days as a change from baseline and compared to control eye drops.*

The secondary objective of Part 3 of the study is:

*to evaluate the efficacy (blink rate, corneal and conjunctival staining) of trehalose emulsion eye drops administered on both eyes three times a day for 30 days as a change from baseline and compared to control eye drops.*

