### **5 Statistical hypotheses**

The purpose of this study is to evaluate ocular safety and tolerability in 3 different study Parts conducted sequentially. For the study part 3 a sample size calculation was conducted with OSDI as the parameter of interest. The evaluation of the study will be based on the total evidence collected.

The null-hypothesis to be tested is

$H_0$  : There is no difference between study products in OSDI scores.

$H_1$  : There is a significant difference in OSDI scores in favour of the investigational product.

Statistical analyses will be performed primarily on the ITT population. The PP population will be used as a secondary dataset.

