## **7 General statistical considerations**

The aim of study is to investigate the safety, ocular tolerability and efficacy of Piiliset Trehalose Emulsion Eye Drop in adult patients with moderate or severe dry eye.

No imputations will be done for missing observations. If not stated otherwise, a two-sided p-value less than 0.05 will be considered statistically significant.

No interim analyses are planned.

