#### **11.1.2. Biomarkers**

Biomarkers to be assessed as primary efficacy endpoints will be determined

- at screening visit;
- before the 1st treatment in all Parts; and
- at end-of-study visit in Parts 2 (Day 10) and 3 (Day 30).

Biomarkers used as primary efficacy endpoints are a part of the physical examination of the eyes and include the following methods:

- tear osmolarity
- tear film break-up time (TBUT)

Ocular comfort ratings (OSDI) by the subjects will be summarized by study day and treatment (Parts 2 and 3). The results will be presented separately for Parts 2 and 3.

The comparisons between treatment groups in Part 2 after ten days treatment will be conducted using standard statistical methodology for paired data (e.g. paired t-test for continuous variables and Wilcoxon signed rank test for variables in ordinal scale) between eyes (study treatment administered in other eye and control treatment to contralateral eye).

The comparisons between treatments in all ocular measurements (including biomarkers and physical examination of eye parameters) in Part 3, which are the primary basis of evaluation of study objectives, are done using the parallel group design. Analysis of variance model will be used to evaluate the difference in the change from baseline in OSDI between treatment groups. Similar method will be used for tear osmolarity and tear film break-up time. In case the normality assumption is violated then Wilcoxon rank sum test will be used instead.

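### Part 3 tests three primary efficacy variables at two-sided 0.05 each, but the SAP omits the promised testing strategy, so the role of the two biomarkers in an efficacy conclusion is open

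*SAP*

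**What the plan says.** The Part 3 primary objective in SAP 2 covers "efficacy (OSDI, tear osmolarity, tear film break-up time) of trehalose emulsion eye drops administered on both eyes three times a day for 30 days", alongside safety and tolerability. SAP 11.1 places all three under primary efficacy variables. SAP 11.1.2 compares change from baseline in OSDI between groups by analysis of variance and extends this to the biomarkers: "Similar method will be used for tear osmolarity and tear film break-up time". A rank sum test replaces it if normality fails.

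The only significance rule is in SAP 7: "If not stated otherwise, a two-sided p-value less than 0.05 will be considered statistically significant".

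Several places single out OSDI:
- The one formal alternative hypothesis (protocol 7.2.3, SAP 5) is "There is a significant difference in OSDI scores in favour of the investigational product".
- Protocol 7.1 sizes Part 3 on OSDI alone.
- The only treatment comparison named under statistical methods in the protocol synopsis is "Changes in OSDI scores in Part 3 will be compared by treatment groups using analysis of variance model".

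Other places widen the basis:
- Protocol 7.2.3 says evaluation is "based on the total evidence collected, not only this single parameter in one Part which was used for sample size calculation". SAP 5 keeps the total-evidence principle.
- SAP 11.1.2 describes the comparisons in all ocular measurements "in Part 3, which are the primary basis of evaluation of study objectives".

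Protocol 7.2.5 deferred the matter: "Details of all methods and the testing strategy will be provided in the SAP finalized before the database lock and randomization code opening". SAP 14 reports no deviations from the protocol's analyses.

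**The concern.** Three variables share the primary label and the same significance threshold. Nothing says how a mixed outcome would be read, for example OSDI not significant and TBUT significant in favour of the emulsion. OSDI alone, any one variable, or all three together could each be defended as the basis for an efficacy conclusion. These rules have different error rates and different power. With none written down, the choice could be made after the results are known. The protocol foresaw the need for a strategy and assigned it to the SAP, so this is an unmet commitment of the plan itself.

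**Working it through.** **Inputs.** Protocol 7.1, Table 3: OSDI at Day 30 of 12 (study treatment) and 24 (control), so a difference of 12; SD 14; two-sided 0.05; power 0.80; 23 completers per group, 46 in total, from 52 randomised. SAP 4: 44 completers (22 per group), given as 83%. Number of primary efficacy variables: 3. The documents give no correlations between the variables, so those below are assumptions.

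**1. The plan's own figure.** The normal approximation gives n = 2(1.960 + 0.842)² × (14/12)² = 21.4, that is 22 per group. The noncentral t calculation uses df = 2n − 2 and noncentrality 12 / (14√(2/n)):
- n = 23: noncentrality 2.907, critical t 2.015, power 81.1%.
- n = 22: noncentrality 2.843, critical t 2.018, power 79.3%.

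The smallest n reaching 80% is 23, so the protocol's 23 per group and 46 in total are reproduced.

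**2. Error rate of the OSDI test alone.** A two-sided 0.05 test gives a false result in favour of the investigational product in 2.5% of trials. The other two tests do not alter this.

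**3. Error rate if any one favourable primary result sufficed.** At zero correlation it is 1 − 0.975³ = 0.073. With correlation, I simulated 200,000 trials per setting with 23 per group, one value per subject, three two-sample t-tests and equal pairwise correlation:

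| Assumed correlation | At least one false favourable result | OSDI alone |
|---|---|---|
| 0 | 7.3% | 2.5% |
| 0.5 | 6.3% | 2.5% |
| 0.9 | 4.2% | 2.5% |

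**4. OSDI truly different (12/14), biomarkers not.** Without an order, at least one false favourable biomarker result occurs in about 5.0%, 4.6% and 3.5% of trials at the same correlations. With OSDI first and the biomarkers in a fixed order, it is at most 2.5%.

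**5. Price of the alternatives.**
- OSDI tested first at 0.05: OSDI power stays at 81%.
- Equal split, 0.05/3 = 0.0167 each: OSDI power falls to 66% at 23 per group, and 80% would need 30 per group.
- Fixed order, if each biomarker truly had the same standardised effect as OSDI (an assumption): the chance of a confirmatory claim falls from 81% for a single test to 66%, 70% and 76% for the first biomarker, and to 54%, 63% and 73% for the second, at correlations 0, 0.5 and 0.9.

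**6. Completer numbers.** 46/52 = 88.5%, in line with the protocol's 88%. 44/52 = 84.6%, not the 83% in SAP 4. At 22 per group, power is just below the stated 80%.

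**The case against.** The strongest reply is that OSDI already is the primary variable in practice. It alone has a hypothesis, a sample-size calculation and a named comparison in the synopsis, and its 5% level is intact. This carries real weight, and it would settle the matter if the documents stopped there. They do not: protocol 7.2.3 expressly declines to rest on that one parameter, and SAP 11.1.2 gives the wider set of measurements primary standing.

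A second reply is that protocol 7.2.3 names ocular safety and tolerability as the main objective, in a single-site study of 64 subjects that never defines an efficacy claim. A missing success rule matters less here than in a confirmatory efficacy trial. This stands and lowers the weight of the point. It does not remove it, because efficacy on the three variables is also part of the Part 3 primary objective and Part 3 is powered on one of them.

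A third reply is that no passage says one favourable result is enough. This also stands. If all three had to succeed, the error rate would not rise; power would fall instead. The figures in step 3 therefore describe one permitted reading. The sentence on all ocular measurements also covers more than three variables, so the calculation applies to the three labelled primary and not to that wider set.

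**Conclusion.** The gap is real and moderate. The promised testing strategy is absent, and the contribution of tear osmolarity and TBUT to an efficacy conclusion is undefined. If any one favourable result were allowed to support a claim, the false-positive chance would be 4.2% to 7.3% instead of 2.5%, over assumed correlations from 0.9 down to 0.

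A reader might infer that the trial as planned has a 7% error rate, or 14% from 1 − 0.95³ = 0.143. The documents do not support this. They never adopt an any-one-suffices rule, and the 14% also counts results against the investigational product, which could not support a claim for it. Nor is there ground for saying that the OSDI test is inflated or the protocol's sample size wrong: that test keeps its level and the 23 per group is reproduced.

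The mismatch between SAP 4 and protocol 7.1 is a separate, small inconsistency. It costs about 2 points of power, from 81% to 79%.

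**What to change.** Add to SAP 11, before database lock and code opening, a Part 3 testing strategy:

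1. Change from baseline in OSDI is tested first at two-sided 0.05.
2. The two biomarkers are then handled in one of two ways, chosen now. Either they are supportive, with no confirmatory claim, or they are tested at two-sided 0.05 in a stated order, continuing only while each result, OSDI included, is significant in favour of the investigational product.
3. All other p-values are exploratory.

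Record this in SAP 14 as a change of emphasis from protocol 7.2.3, which declines to rest on OSDI alone. It is more than a clarification.

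In SAP 4, either restore 46 completers (23 per group, 88%) as in protocol 7.1, or keep 44 and restate power as 79% at 22 per group and completion as 85%.

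The cost is wording only: the number of subjects and OSDI power do not change. The real price is that a confirmatory biomarker claim depends on OSDI succeeding first, or is given up under the supportive option. An equal alpha split would avoid that dependence, but at the loss of OSDI power shown in step 5, so it is the less attractive choice at this sample size.

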## 11.2 Secondary efficacy variables

The secondary efficacy parameters include the following assessments:

### 11.2.1. Biomarkers

Biomarkers to be assessed as secondary efficacy endpoints will be determined

- at screening visit;
- before the 1st treatment in all Parts; and
- at end-of-study visit in Parts 2 and 3.

The biomarkers are a part of the physical examination of the eyes and include the following methods:

- blink rate (blinks per minute)
- corneal staining (Oxford grading)
- conjunctival staining (Oxford grading)

Blink rate is further converted to the interblink interval (IBI) and used with TBUT for calculation of the ocular protection index ( $OPI = TBUT/IBI$ ) (Ousler et al. 2008).

Similar methods than in the primary variables will be used for the secondary variables. ANOVA model will be used for blink rate and Wilcoxon rank sum test will be used for the staining variables.

## 12 Analysis of safety and tolerability

The safety population having received the study treatment and with any follow-up data will be considered evaluable for safety and tolerability for the corresponding Part of the study.

In Part 1, the ocular safety and tolerability of trehalose emulsion eye drops will be evaluated as a within-subject comparison to the untreated eye and to baseline. In Part 2, the evaluation will be performed as a within-subject comparison to the control eye and to baseline. In Part 3, the evaluation will be performed between subjects receiving trehalose emulsion eye drops in comparison with subjects receiving control eye drops and to baseline.

---

Physical examination of the eye parameters will be summarized descriptively by eye in all Parts of the study. The ocular safety and tolerability of the treatments evaluated at the end-of-study visit will be summarized by study day, treatment and eye.

#### A. Physical examination of the eyes

Physical examination of the eyes will be performed

- at screening;
- in Part 1 at baseline (before the 1st dose) and after the 4th dose;
- in Part 2 at baseline (Day 1, before the 1st dose) and after the last dose; and
- in Part 3 at baseline (Day 1, before the 1st dose) and after the last dose.

Methods:

- Visual acuity (ETDRS)
- Digital photography of the anterior eye
- Bulbar redness (IER grading)
- Lid redness (IER grading)
- Intraocular pressure (IOP)

If feasible statistical analysis using similar methods than for efficacy variables can be conducted for these parameters.

### **12.1 Adverse events**

AEs will be summarized for each treatment group and study Part by severity, causality, and duration. Ocular AEs will be reported separately. All SAEs (including SADE and USADE) will be listed with all relevant information.

### **13 Completion and premature discontinuation**

Completion and premature discontinuation will be listed and the reasons for premature discontinuation will be presented.

### **14 Deviations from the analyses planned in the study protocol**

There are no deviations from analyses planned in the protocol.

### **15 Execution of statistical analyses**

Statistical analyses will be performed by 4Pharma Ltd.

**16 Hardware and software**

Statistical analysis, tables and patient data listings will be performed with SAS® version 9.4 for Windows (SAS Institute Inc., Cary, NC, USA).

